Investigational product/comparator (*State the devices / products that will be investigated // used and for comparative studies also the comparator/s*)

1. Cone beam CT full facial scan on every patient before and after implant placement on surgical site single arch at 1 year, 2 year, 3 year follow up (i-CAT \$600 per patient x40 = \$ 24,000)
2. Facilitate Pro software convert Dicom images for implant placement design and surgical stent fabrication (\$12,000)
3. Surgical tools for implant placement:
 (syringe, needles, elevators, periotomes, extraction forceps #150 & #151, bone spreading chisels, bone grinder, bone trap, bone compactor, bone curette, osteotomes, resorbable and non-resorbable sutures, needle holders, scissors
 Surgical stent, two surgical bundles, two surgical trays, one surgical motor, two surgical handpiece heads, two full restorative trays and bundles, surgical saline bags for surgical irrigation, disposable irrigation kits for drill unit, disposable drills. Pulse oximetry) (\$ 30,000)
4. Root form implants of various sizes, cover screws (\$250 per implant x est. 80 = \$ 20,000)
5. Freeze dried demineralised bone as bone graft material (\$ 100/ 0.5cc vial x est.20 = \$ 2,000)
6. Resorbable membrane (\$ 100/ membrane x est. 20 = \$ 2,000)
7. Poly vinyl siloxane impression materials (\$ 4,000)
8. Prosthodontic instrument kits plus laboratory fee (impression transfer material, implant abutments, implant analogues, Cresco Precision system)
 (\$ 400 per implant restoration x est. 80 = \$32,000)
9. Two WhipMix Semi- adjustable articulators (\$ 800 x 2 = \$1,600)
10. Half-time patient coordinator (\$ 18,000 or neg.)
- *11. Computer for information storage and portable printer (\$ 3,000)
12. SLR camera with Macro-lens and flash (\$ 2,500)
13. Histological examination of 40 bone biopsies processed at UAB Anatomic Pathology Lab, including special stains and decalcification (\$ 8,000)
14. Processing of failed implants at the UAB Bone Core facility with subsequent histologic examination of implant-bone interface (\$200.00 per failed implant x est. 5 = \$1,000)
15. Journal publication expenses (\$2000.00)
16. Travel expenses to national and/or international meetings by the PI investigator and one co-investigator (\$ 4000.00)

Total budget: \$166,000

Outcome variables (Indicate which variable is the primary variable for the study)

Efficacy (*List all efficacy variables and indicate clearly your primary outcome variable*)

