The primary variable examined will be the treatment outcome as measured according to the Albrektsson and Zarb criteria for implant success. Patients will be examined at each interval for the presence of pain, infection, mobility, and radiographic bone height of each implant

Additional clinical assessments (*Describe use of any additional clinical assessments e.g. clinical photographs etc.*)

1. All selected patients will have prior medical authorization to have surgical procedure performed. Patients will undergo complete oral clinical examination as well as cone beam CT scan, selected periapical and vertical bitewing radiographs on planning implant placement site, full mouth photography, diagnostic casts, and surgical stent before implant placement.
2. Cone Beam CT on the implant sites of arches at 1 year, 2 years and 3 years post placement follow-up (Cone Beam CT provides 1:1 ratio image, view in 3- dimensions, limited radiation exposure). The images will be evaluated by the dental radiologist.
Compare accuracy and efficiency of Cone Beam CT image of alveolar bone around implant in 3-dimensions vs. of conventional standard X-ray examination of bone lost around implant in 2-dimensions.
3. Histologic examination of the bone biopsy from the implant sites will provide scientific evidence of the bone changes that may occur in the process of implant osteointegration under immunocompromised conditions.
4. Photograph during implant restoration procedure and after complete restoration.
5. Patient post-implant restoration survey (such as: general satisfaction, social life, mastication on hard food, comfort).

Statistical methods (*Describe as relevant the statistical methods to be used, the populations to be analysed (e.g. intention to treat, per-protocol), and any interim analyses*)

Descriptive statistics will be applied to acquire the mean parameter values, range, and implant success rate as determined by the Albrektsson and Zarb criteria.

With rigorous inclusion/exclusion criteria proposed, parametric data will be analysed using ANOVA methods. Nonparametric (yes/no) criteria will be analyzed with the Chi-Square method.

Publications / Presentations (*Describe your plans with regard to publications or public presentations i.e. what journals or conferences/meetings*)

Peer reviewed journals such as: Journal of American Dental Association, Journal of Prosthodontics, Journal of General Dentistry.

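### The plan names ANOVA and chi-square for data read on each implant but states neither the unit of analysis nor a primary visit; testing implants as independent would make the bone-height intervals for the HIV comparison too narrow.

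*Combined protocol and SAP*

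**What the plan says.** The primary variable is implant success by a published set of criteria (Outcome variables, Efficacy). The measurement is set out as follows: "Patients will be examined at each interval for the presence of pain, infection, mobility, and radiographic bone height of each implant". Bone height is therefore an implant-level reading. Yearly timing is explicit only for one method (Additional clinical assessments, item 2): "Cone Beam CT on the implant sites of arches at 1 year, 2 years and 3 years post placement follow-up".

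The Statistical methods section first lists descriptive summaries, "mean parameter values, range, and implant success rate", and then gives its only inferential sentences: "parametric data will be analysed using ANOVA methods. Nonparametric (yes/no) criteria will be analyzed with the Chi-Square method".

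The comparison is between 20 HIV-positive and 20 HIV-negative patients (Study centre(s) and number of subjects planned). The documents do not fix the number of implants per patient:
- The Target patient population section allows bridges on two implants and also single crowns.
- Under Investigational product/comparator, item 4 budgets implants as "per implant x est. 80" and item 8 budgets restorations as "per implant restoration x est. 80".
- Item 13 budgets "Histological examination of 40 bone biopsies", although Objectives item 3 plans a biopsy at every implant site.

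No section states the unit of analysis, a primary visit, a significance level, or how correlation between implants in one mouth is handled.

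**The concern.** HIV status varies between patients, never between implants in the same mouth. Two implants in one patient share that patient's bone, hygiene, immune state and surgeon, so their outcomes are likely to be positively correlated. Ordinary one-way ANOVA and the chi-square test treat every row as independent. Applied to a data set with one row per implant, they would credit the HIV comparison with more information than 40 patients supply. The standard error for bone height would be too small, and two failures in one mouth would count as two independent events.

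The missing primary visit is a related gap. With readings at 1, 2 and 3 years and none singled out, the headline comparison can be chosen after the results are seen. No size is put on this part, because the plan does not say whether visits would be tested separately, pooled or summarised.

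**Working it through.** The plan contains no power calculation, significance level or variance, so there is no statistical figure of its own to reproduce.

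**Inputs from the documents.** 40 patients, 20 per group; an estimated 80 implants; for illustration, the laboratory line for failed implants, "per failed implant x est. 5" (item 14). That line is a cost estimate, not an expected failure rate.

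**Assumptions not in the documents.** Two-sided 5% level; within-patient correlation (ICC) of 0.1, 0.3 or 0.5; exactly two implants in every patient.

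**Step 1, cluster size.** 80/40 = 2 implants per patient on average. If the 40 biopsies were one per implant site, the same division would give 40/40 = 1, so the figure of 2 is uncertain.

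**Step 2, bone height with implants tested as independent.** Design effect = 1 + (m − 1) × ICC with m = 2. The true standard error is √(design effect) times the implant-level one. The true error of a nominal 5% test is approximately 2 × [1 − Φ(1.96/√(design effect))].

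| ICC | Design effect | SE ratio | Type I error |
|---|---|---|---|
| 0 | 1.0 | 1.00 | 5.0% |
| 0.1 | 1.1 | 1.05 | 6.2% |
| 0.3 | 1.3 | 1.14 | 8.6% |
| 0.5 | 1.5 | 1.22 | 11.0% |

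Simulation of 20 against 20 patients with two implants each (200,000 null trials per setting) gives 5.0, 6.3, 8.7 and 11.1%. The same data reduced to one mean per patient give about 5% in every setting. If half the patients have one implant and half have two, the implant-level errors are 4.9, 5.8, 7.5 and 9.1%. With one implant each, the error is 5.0% throughout.

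**Step 3, success tested by implant.** Exact enumeration, 20 against 20 patients, two correlated implants each:
- At 5/80 = 6.25% failing, the uncorrected chi-square has size 5.3, 6.3, 8.6 and 11.2% at ICC 0, 0.1, 0.3 and 0.5.
- At the same rate, with the Yates correction, it is at most 2.6%.
- At 2.5% failing, even the uncorrected test is at most 4.3%.

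**Step 4, can the unit change a conclusion on success?** Take five failed implants in one group and none in the other, with the uncorrected chi-square, N(ad − bc)²/(product of the four margins).
- By implant, 5/40 against 0/40: 80 × 200²/(40 × 40 × 5 × 75) = 5.33, p = 0.021.
- By patient, failures in five mouths (5/20 against 0/20): 40 × 100²/(20 × 20 × 5 × 35) = 5.71, p = 0.017.
- By patient, four mouths: 40 × 80²/(20 × 20 × 4 × 36) = 4.44, p = 0.035.
- By patient, three mouths: 40 × 60²/(20 × 20 × 3 × 37) = 3.24, p = 0.072.

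With this test held fixed, the choice of unit moves the result across 5% only when the five failures fall in three mouths.

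**The case against.** The plan never says that implants will be tested as independent. The implant success rate appears in the descriptive sentence, and the test sentences name no unit. The word for ANOVA is general enough to cover a nested or repeated-measures form. The correlation and the 5% level are assumed, and two implants per patient rests on cost lines that the biopsy count does not match. Bone height, where the effect is clearest, is one of several items examined and is not itself named as the primary variable.

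Most of this stands. A reader might infer that the plan prescribes an invalid implant-level analysis; the text does not support that, because it leaves the analysis open. A reader might also infer that the primary success comparison is bound to be anti-conservative. That does not follow either: the direction depends on the chi-square variant and on the failure rate, as step 3 shows.

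What does not stand is that the wording is sufficient. Repeated measures over visits would not by themselves deal with two implants in one mouth, and the chi-square sentence has no comparable clustered reading. The data are collected by implant, so applying the named methods to them as collected is a natural course that nothing in the plan prevents.

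**Conclusion.** The omission is certain: the unit of analysis and the primary visit are not stated anywhere. The harm is conditional. It arises if implants are tested as independent, if a good share of patients have more than one, and if outcomes within a mouth are correlated. Under the assumptions listed, the bone-height error is modest at ICC 0.1 and roughly double the nominal level at ICC 0.5, and it vanishes with one implant per patient. For success, the unit matters mainly when several failures share a mouth. The point is a cheap improvement, not evidence that the study's comparison is wrong.

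**What to change.** In Statistical methods:
- State that the patient is the unit of inference for the HIV comparison, name one primary time point, and give the significance level.
- Analyse bone height by ANOVA on one mean per patient at that time point, or by a mixed model with random effects for patient and for implant within patient.
- Compare success by patient (any failed implant, yes or no) with an exact test, because failures are likely to be few.
- Report implant-level success rates descriptively.

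**Cost.** A few sentences, with no new patients or measurements. With two implants each, bone-height intervals become wider by √(design effect) × t(38 df)/t(78 df), with 2.024/1.991 = 1.017: 1.049 × 1.017, 1.140 × 1.017 and 1.225 × 1.017, or about 7, 16 and 25% at ICC 0.1, 0.3 and 0.5. This is the price of correct coverage.

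The exact test of success is conservative and has low power. At 6.25% of implants failing, its true size is 1.0 to 1.6% over ICC 0 to 0.5. Five affected patients against none gives p = 0.047, and four against none gives 0.106. Even 0/20 affected patients leaves an upper 95% limit of 16.8%. The plan should say so and rest on estimates and intervals as well as the test.

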APPENDIX 2 - Details of products to be provided:

Investigator name: [name], UAB

Study Title: Longitudinal Study of Dental Implant Therapy in HIV Positive Patients

Astra Tech reference no.: D-2007-51

Product	Ref. no.	Quantity
Restorative Instrument Kit	24879	2
Restorative Tray	22495	2
Torque Wrench Kit	24100	2
Torque Wrench Bit.Locator-15mm	24490	2
Wrench Adapter	24572	2
Implant Unit SI-915, 115 V	24360	2
Cont Ang. W&H WS-75 E/KM AE	22903	2
Surgical Instrument Kit	24878	2
Driver Handle	24358	2
Surgical Tray	24349	2
Ratchet Wrench	24357	2
Hex Screwdriver, Short	22514	4
Hex Screwdriver, Intermediate	22515	4
Osteotome Kit	22956	2
SP Drill Kit, Short	22898	24
SP Drill Kit, Long	22899	24
SP Twist Drill, 3.35 mm, Short	22908	12
SP Twist Drill, 3.35 mm, Long	22909	12
SP Twist Drill, 3.7 mm, Short	22910	24
SP Twist Drill, 3.7 mm, Long	22911	24
SP Conical Drill, 4.5mm, Short	22921	24
SP Conical Drill, 4.5mm, Long	22922	24
SP Conical Drill, 5.0mm, Short	22923	24
SP Conical Drill, 5.0mm, Long	22924	24
OsseoSpeed 3.5 S - 9 mm	24611	8
OsseoSpeed 3.5 S - 11 mm	24612	8
OsseoSpeed 3.5 S - 13 mm	24613	8
OsseoSpeed 4.0 S - 9 mm	24621	8
OsseoSpeed 4.0 S - 11 mm	24622	10
OsseoSpeed 4.0 S - 13 mm	24623	8
OsseoSpeed 4.5 - 9 mm	24631	8
OsseoSpeed 4.5 - 11 mm	24632	10
OsseoSpeed 4.5 - 13 mm	24633	8
OsseoSpeed 5.0 - 9 mm	24641	8

OsseoSpeed 5.0 - 11 mm	24642	8
OsseoSpeed 5.0 - 13 mm	24643	8
Implant Transfer 3.5/4.0 Short	24547	30
Implant Transfer 3.5/4.0 Long	24548	20
Fixt. Transfer 4.5/5.0,Short	22433	30
Fixt. Transfer 4.5/5.0, Long	22485	20
Implant Replica 3.5/4.0	24276	50
Implant Replica 4.5/5.0	22509	50
Ti-Zir Design 3.5/4.0 Try-in	24847	4
Ti-Zir Design 4.5/5.0 Try-in	24849	4
TiDesign 3.5/4.0 - Ø 5.5,1.5mm	24287	12
TiDesign 3.5/4.0 - Ø 5.5, 3mm	24288	12
TiDesign 4.5/5.0 -Ø5.5,1.5 mm	24235	12
TiDesign 4.5/5.0 -Ø5.5, 3mm	24236	12
ZirDesign 3.5/4.0 Ø 4.5 1.5 mm	24702	8
ZirDesign 3.5/4.0 Ø 5.5 1.5 mm	24704	8
ZirDesign 4.5/5.0 Ø 5.5 1.5 mm	24707	8
ZirDesign 4.5/5.0 Ø 5.5 3 mm	24708	8
Dir.Abutm.API 3.5/4.0-Ø5, 1mm	24555	4
Dir.Abutm.API 3.5/4.0-Ø5.2.5mm	24556	4
Dir.Abutm.API 4.5/5.0-Ø5, 1mm	24559	4
Dir.Abutm.API 4.5/5.0-Ø5.2.5mm	24560	4
Dir.Abutm.API 4.5/5.0-Ø6, 1mm	24562	4
Dir.Abutm.API 4.5/5.0-Ø6.2.5mm	24563	4
Cover Screw 3.5/4.0 - 0 mm	24328	40
Cover Screw 4.5/5.0 - 0mm	24447	40
Healing Abutm.3.5/4.0-Ø4.2mm	24574	12
Healing Abutm.3.5/4.0-Ø4.5.4mm	24575	12
Healing Abutm.3.5/4.0-Ø5.5.2mm	24577	12
Healing Abutm.3.5/4.0-Ø5.5.4mm	24578	12
Healing Abutm.4.5/5.0-Ø5.5.2mm	24582	12
Healing Abutm.4.5/5.0-Ø5.5.4mm	24583	12
Healing Abutm.4.5/5.0-Ø6.5.2mm	24585	12
Healing Abutm.4.5/5.0-Ø6.5.4mm	24586	12
Bone Trap	22179	8
Disposable Irrigation Set	22176	8
Periotome,straight/curved edge	24274	2
Periotome, curved/straight	24275	2
Grinding Handle	22740	2
Bowl, Titanium	22137	4
Forceps 94	22437	4

Facilitate Instrument Kit	24819	2
Direct Abutment 3.5/4.0 Try-in	24848	4
Direct Abutment 4.5/5.0 Try-in	24850	4

Products will be distributed to the below contact person and address:

[name] [name]
Comprehensive Dentistry Department
[name]
[name]
